2.2. Secondary Objectives

- To evaluate the impact of an HT boost on acute and late toxicity.
- To evaluate the influence of HTIMRT to health-related quality of life (HRQOL), prostate cancer-specific anxiety and prostate cancer-specific QOL.
- To quantify biomarker expression in different prostate tumor regions, comparing specifically the functional MRI suspicious regions to those that are not suspicious.
- To evaluate the incidence and relationship of circulating free DNA and tumor cells to tissue biomarkers and prostate biopsy positivity at 2 years after completion of therapy.
- To record other biochemical failure, clinical failure and mortality endpoints.

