5.2 Evaluations During Treatment

- Weekly history and physical exam (mainly skin reaction assessment beginning after 5 days of therapy) (Zubrod performance status; Karnofsky or ECOG performance status may be used to estimate Zubrod).
- Blood will be drawn during the last week of RT from a vein for the following tests:
 - Serum Testosterone.
 - Liver function tests.
 - Complete cell counts.
 - Lipid profile.
- Research fluids consisting of plasma and serum (up to 4 tubes) and approximately 50 ml urine will be obtained during the last week of RT, if possible.
- Psychosocial questionnaires during the last week of RT
 - The Expanded Prostate Cancer Index Composite Questionnaire-SF12 (EPIC/SF12).
 - Memorial Anxiety Scale for Prostate Cancer patients (MAX-PC).
 - International Prostate Symptom Score (IPSS).

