10.0 MEASUREMENT OF TOXICITY

Acute proctitis and cystitis lasting for up to 3 months after completion of radiotherapy are accompaniments of radiotherapy for carcinoma of the prostate. The severity of these reactions is routinely evaluated during treatment and will be scored according to the criteria outlined in Appendix II. In our extensive experience, grade 3 or 4 acute toxicities are rare.

Delayed toxicities are usually related to urinary, rectal, and sexual function. The anticipated urinary and rectal toxicities and severity criteria are those shown in Appendix II. Other untoward clinical events will, however, also be documented.

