Finally, to assess the prognostic value of 2-year post treatment biopsy findings, we will further study patients who had this procedure without prior evidence of biochemical or clinical failure. Taking the date of biopsy as the start of follow up, we will analyze subsequent failure rates and failure-free survival and test for association with biopsy positivity and treatment arm.

QOL scores will be calculated in accordance with established scoring methods for each instrument. Descriptive summaries of scores at baseline and each subsequent follow up will include median and range, means and standard deviations. Where criteria for clinically meaningful differences have been established, we will also categorize changes in these scores (computed by subtracting baseline from subsequent score) as indicating improvement,

worsening, or no change and summarize these by counts and percentages. Comparison by treatment arm at baseline and at treatment completion will be based on t-test (average score) and Fisher's exact test (percent improved). Further analysis allowing for repeated measurement will be conducted using mixed models.

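### The quality-of-life responder test compares percent improved at the end of radiotherapy, so for the EPIC urinary and bowel domains it is a poor measure of harm

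*Combined protocol and SAP*

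**What the plan says.** Section 2.2 makes quality of life a secondary objective: "To evaluate the influence of HTIMRT to health-related quality of life (HRQOL), prostate cancer-specific anxiety and prostate cancer-specific QOL". Where meaningful-difference criteria exist, section 14.5 will "categorize changes in these scores (computed by subtracting baseline from subsequent score) as indicating improvement". Decline and stability are the other two classes, and all three are tabulated. The arm comparison follows: "Comparison by treatment arm at baseline and at treatment completion will be based on t-test (average score) and Fisher's exact test (percent improved"). Later visits are covered by one sentence: "Further analysis allowing for repeated measurement will be conducted using mixed models". It names no domain, visit or contrast.

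The treatment-completion assessment is fixed by section 5.2: "Psychosocial questionnaires during the last week of RT". Section 10.0 states what to expect then: "Acute proctitis and cystitis lasting for up to 3 months after completion of radiotherapy are accompaniments of radiotherapy for carcinoma of the prostate". Section 4.11 adds that most patients have urinary or bowel symptoms, of grade 2 or lower, during and after treatment.

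Section 14.5 makes arm comparisons one-sided at 5%, without a direction for quality of life. The listed hypotheses expect no significant quality-of-life difference (hypothesis 4) and less anxiety with HTIMRT (hypothesis 5).

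**The concern.** Of the three change categories, only improvement gets an arm test. That suits MAX-PC, where hypothesis 5 predicts improvement. It does not suit the EPIC urinary and bowel domains, where the question about a focal boost is whether it adds to decline. A test of percent improved counts an unchanged man and a worsened man alike, so two arms can differ widely in decline and still give the same responder result.

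The two stated times make this worse. At baseline a change from baseline does not exist. At treatment completion the protocol's own account points towards worse scores, not better ones. No planned arm test asks how many men have a meaningful patient-reported decline, and for that reader the responder result would be the natural figure to look at.

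**Working it through.** **Inputs from the documents.** 36 per arm and a one-sided 5% Fisher's exact test (14.2); one-sided 5% arm comparisons (14.5). The documents give no expected improved or worsened share, no change-score SD and no threshold. All such values below are assumptions.

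**Method.** Exact power is the sum, over all pairs (x, y), of Bin(x; 36, p1) × Bin(y; 36, p2) for those tables whose one-sided hypergeometric p-value is at most 0.05.

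**The plan's own figure.** For 52.5% v 22.5% this gives 80.3%, against the stated 80%. The method therefore reproduces section 14.2, which holds the plan's only power figure. None is given for quality of life.

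**Check 1: pooling unchanged with worsened.** Assume 5% improve in each arm, and 40% (SIMRT) v 70% (HTIMRT) worsen. Unchanged is then 100 − 5 − 40 = 55% v 100 − 5 − 70 = 25%.
- Percent improved, 5% v 5%: rejection 0.6%.
- Percent worsened, 70% v 40%: power 79.5%.

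**Check 2: how sparse counts limit the test.** If nobody improves in one arm, the other needs 5 of 36 (14%) improved to reach p = 0.027; 4 of 36 gives p = 0.057. Power is 3.2% for 5% v 0% improved, 28.9% for 10% v 0%, and 7.1% for 10% v 5%.

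**Check 3: one true harm, three tests.** Assume normal change scores with SD 1, higher meaning better, a meaningful-change threshold of 0.5 SD, mean change m in SIMRT and m − 0.6 in HTIMRT. For an arm with mean change μ:
- improved = 1 − Φ(0.5 − μ)
- worsened = Φ(−0.5 − μ)

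| SIMRT mean m | Improved, SIMRT v HTIMRT | Power | Worsened, SIMRT v HTIMRT | Power |
|---|---|---|---|---|
| −0.5 SD | 15.9% v 5.5% | 25.3% | 50.0% v 72.6% | 56.6% |
| −0.75 SD | 10.6% v 3.2% | 13.8% | 59.9% v 80.2% | 50.4% |
| −1.0 SD | 6.7% v 1.8% | 5.0% | 69.1% v 86.4% | 44.7% |

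The planned t-test does not depend on m. Its noncentrality is 0.6 × √(36/2) = 2.546 on 70 degrees of freedom, with critical value 1.667, which gives 80.9% power.

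**Reading.** In each row percent worsened is stronger than percent improved, and the t-test is stronger than both.

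**The case against.** The strongest reply is that the quoted sentence also plans a t-test on average score at the same visit, and that test uses all movement in the score. If 80% v 50% worsen and change scores are normal with equal SD, the shift is 0.84 SD; the t-test then has 97% power, against 81% for percent worsened. The plan also has mixed models over questionnaires running to 5.25 years, tabulated worsening, and Gray's test on grade 2+ and 3+ GI and GU toxicity. All of this stands. A reader might infer that the plan cannot show harm, or that it is bound to agree with hypothesis 4. The documents support neither inference; both would need the responder test to be the only quality-of-life analysis.

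A reader might also take the improved category to be nearly empty. The documents expect symptoms but do not say how many men cross a meaningful-change threshold in either direction. In the normal model, if SIMRT scores fall by only 0.25 SD or not at all, 22.7% or 30.9% of SIMRT men improve. Percent improved then has 36.2% or 44.7% power for a 0.6 SD harm, still below the 59.7% or 58.4% for percent worsened.

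The baseline wording can be read charitably as covering average scores only, since a responder test there cannot be run. Nor is it clear that the rule covers IPSS: section 1.5 describes that scale, but the definition of QOL in section 9.1 lists only EPIC-SF12 and MAX-PC.

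What the reply does not do is repair the responder test. The t-test compares means, Gray's test uses toxicity grades, and the mixed models name no contrast.

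**Conclusion.** The point holds for the responder test alone. For the EPIC urinary and bowel domains, percent improved is the wrong category to test at the end of radiotherapy, and at baseline it is undefined.

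For a 0.6 SD harm with a 0.5 SD threshold, and SIMRT scores falling by 0.5 to 1.0 SD on average, percent improved has about 5–25% power, percent worsened 45–57%, and the planned t-test 81%. These figures rest on the normal model and the assumed thresholds and declines. The pooling of unchanged with worsened men does not depend on them, because it follows from the wording. This is a secondary analysis; the primary endpoint and the sample size are unaffected.

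**What to change.** In section 14.5:
- For the EPIC urinary and bowel domains, compare percent worsened by arm, using the established meaningful-change criterion, at treatment completion and at the yearly questionnaire nearest 2 years after radiotherapy. Under section 5.3 (15 months, then yearly) that is 15 + 12 = 27 months. Name the visit in months, because footnote (e) of the study calendar words the schedule differently.
- Present this as a supplement to the t-test and mixed models, not as a replacement.
- Keep percent improved for MAX-PC.
- Limit the baseline comparison to average scores.
- State the direction of each one-sided test, and say whether the responder rule applies to IPSS.

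The cost is a wording change. The categories and questionnaires are already planned, so no new data are needed. The downside is one more secondary comparison per domain, which should be reported as having no multiplicity control.

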3.0 PATIENT SELECTION

3.1 Inclusion (Eligibility) Criteria

- A. Biopsy confirmed adenocarcinoma of the prostate.
- B. T1-T3a disease based on digital rectal exam.
 - a. T1a is permitted if peripheral zone biopsies are positive.
 - b. T3a disease based on MRI is acceptable.
- C. No evidence of metastasis by any clinical criteria or available radiographic tests.
- D. Gleason score 6-8.
- E. Patients with Gleason score 8 must be offered long term androgen deprivation therapy (ADT) and refuse such treatment because only 4-6 (± 2 months) months (short term ADT) is permitted on this protocol. Gleason score ≥ 8 patients should be

recommended to receive short term ADT in conjunction with RT. When given, the ADT recommended to begin after fiducial marker placement, if applicable; however, ADT is permitted to have been started up to two months prior to the signing of consent.

- a. Patients with Gleason score 8 disease must have <40 of the diagnostic tumor tissue involved with tumor.
- b. Patients with Gleason score ≤ 7 may be treated with 4-6 (± 2 months) months of ADT.
- F. PSA ≤ 100 ng/mL within 3 months of enrollment. If PSA was above 100 and dropped to ≤ 100 with antibiotics, this is acceptable for enrollment.
- G. If PSA is >15 ng/ml or there is \geq Gleason 8 disease, a bone scan should be obtained ≤ 4 months before enrollment and should be without evidence of metastasis. A questionable bone scan is acceptable if plain x-rays, CT and/or MRI are negative for metastasis.
- H. No previous pelvic radiotherapy
- I. No previous history of radical/total prostatectomy (suprapubic prostatectomy is acceptable)
- J. No concurrent, active malignancy, other than non-metastatic skin cancer or early stage chronic lymphocytic leukemia (well-differentiated small cell lymphocytic lymphoma). If a prior malignancy is in remission for ≥ 5 years then the patient is eligible.
- K. Identifiable multiparameter functional MRI defined tumor lesion or lesions using a 1.5T or 3.0T MRI (3.0T preferable), that total in volume $<33\%$ of the prostate within 3 months prior to enrollment.
 - a. Multiparametric functional including DWI of prostate and pelvis is required prior to protocol consideration
- L. Ability to understand and the willingness to sign a written informed consent document
- M. Zubrod performance status <2 (Karnofsky or ECOG performance status may be used to estimate Zubrod)
- N. Willingness to fill out quality of life/psychosocial forms.
- O. Age ≥ 35 and ≤ 85 years.

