5.0 CLINICAL AND LABORATORY EVALUATIONS

5.1 Baseline/pretreatment Evaluations

- History and physical exam, including evaluation of patient's ability to perform daily activities (Zubrod performance status Karnofsky or ECOG performance status may be used to estimate Zubrod), within 8 weeks prior to protocol entry.
- Blood tests: within 3 months prior to protocol enrollment unless otherwise indicated.
 - PSA Level.
 - Liver function tests.
 - Complete blood cell counts.
 - Lipid Profile

- Testosterone level - Serum testosterone will be drawn within 4 months of enrollment . This is only applicable to patients not started on ADT prior to signing consent. Patients who have been started on ADT prior to signing consent are not required to have a serum testosterone at this level prior to signing consent; but, a serum testosterone prior to fiducial marker placement is recommended.
- Bone scan (depending on PSA level and Gleason score) within 4 months of protocol enrollment.
- Multiparametric functional MRI of prostate/pelvis using a 1.5 or 3.0T MRI (preferably 3.0T) within 3 months prior to protocol enrollment.
- A pathology review at the University of Miami of the outside biopsy material prior to enrollment.
- Research fluids of plasma and serum (up to 4 tubes total) and approximately 50 ml urine will be obtained prior to fiducial marker placement, if possible after signing consent form.
- Psychosocial questionnaires after enrollment and prior to fiducial marker placement or randomization
 - The Expanded Prostate Cancer Index Composite Questionnaire-SF12 (EPIC-SF12).
 - Memorial Anxiety Scale for Prostate Cancer patients (MAX-PC).
 - International Prostate Symptom Score (IPSS).
- Gold marker placement, if applicable. and prostate biopsies (optional) within 4 weeks after enrollment CT and MRI simulation.

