14.4 Stratification Factors

Patients will be randomized in equal proportion to receive either HTIMRT or SIMRT using a permuted block design stratified by baseline PSA (<10 vs 10 to \leq 100), Gleason score (6-7 vs 8-10) and short term (4 to 6 months) androgen deprivation (STAD) therapy (Y vs. N). Where appropriate, these factors will be used in the analysis of study data; for example, to stratify statistical tests comparing treatment arms or to adjust regression models. We note that STAD therapy will be recommended for all Gleason 8 patients; however, we allow for all eight possible combinations as strata in order to ensure equal treatment allocation in the event that enrollment includes a small number of patients with uncommon combinations of these factors.

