14.5 Analysis plan

The main analysis of study findings will be done by treatment assignment (intention-to-treat) in all patients who meet evaluable criteria as stated in Section 14.3. We will report any instances of treatment crossover. As noted above, analyses of some secondary endpoints, including acute toxicity, psychosocial parameters, tissue and blood product-related biomarker distribution on ultrasound-guided biopsies, and initial MRI findings may be reported before the efficacy endpoints, including the primary endpoint. These secondary endpoints will be analyzed after all planned patients have been accrued, completed treatment and have a minimal potential follow-up of 3 months from the end of RT. An initial analysis of clinical outcome (efficacy) is

planned after all patients have been assessed for two year post treatment failure status and a final analysis will be done at the completion of the planned 5 year follow up of all study patients. Statistical tests comparing treatment arms will be one-sided with 5% significance level and stratified where appropriate by the factors considered in randomization.

Statistical analysis will include descriptive statistics for patient demographics and baseline disease characteristics, both overall and by treatment arm. Counts and percentages will be used to summarize the distribution of categorical variables while median, range, mean and standard deviation will be used for continuous variables. Baseline characteristics will include age, sex, race/ethnicity, T-category, Gleason score, PSA, risk group and performance status. Biomarker measurements and proteomic/genomic profiles obtained from baseline biopsy will also be summarized with descriptive statistics. (76)

Treatment received will be summarized by the type of RT and STAD components of therapy, the number and duration of treatment delays, and the rates of discontinuation or completion. Summaries will be provided for each treatment arm. Safety analysis will include a detailed tabulation of acute and late occurring toxicity by type and grade, both overall and by treatment arm. Additionally, we will estimate the cumulative incidence (from start of treatment) of grade 2+ and 3+ genitourinary (GU) toxicity and of grade 2+ and 3+ gastrointestinal (GI) toxicity in each treatment arm. Death without the toxicity of interest will be treated as a competing risk, and toxicity rates will be compared by treatment arm using Gray's test. (77, 78)

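### The comparison of mean QOL and anxiety scores at treatment completion leaves out the baseline score: valid, but less precise than the scheduled data allow

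*Combined protocol and SAP*

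**What the plan says.** Section 14.5 (Analysis plan) gives the QOL comparison in one sentence: "Comparison by treatment arm at baseline and at treatment completion will be based on t-test (average score". The sentence goes on to pair the t-test with Fisher's exact test on the percentage of patients improved. One t-test serves both time points, so it is a test of the scores themselves and not of change.

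Change from baseline enters in one place, a classification into improved, worse or unchanged, and only conditionally: "Where criteria for clinically meaningful differences have been established, we will also categorize changes in these scores". Section 14.5 then adds: "Further analysis allowing for repeated measurement will be conducted using mixed models". No model terms are given.

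On sidedness and adjustment, Section 14.5 states: "Statistical tests comparing treatment arms will be one-sided with 5% significance level and stratified where appropriate by the factors considered in randomization". Section 14.4 says that the same factors may be used "to stratify statistical tests comparing treatment arms or to adjust regression models". They are PSA, Gleason score and short-term androgen deprivation; the baseline QOL score is not among them.

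The baseline score should nonetheless exist. Section 5.1 schedules "Psychosocial questionnaires after enrollment and prior to fiducial marker placement or randomization", Section 5.2 schedules "Psychosocial questionnaires during the last week of RT", and Section 3.1 makes it an eligibility criterion: "Willingness to fill out quality of life/psychosocial forms".

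**The concern.** A patient's score before treatment usually predicts part of his score at the end of treatment. A t-test on end-of-treatment scores leaves that predictable part in the error term. In a trial of 72 to 76 patients, the standard error is then larger than it need be, and any chance difference between the arms at baseline is partly carried into the result.

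QOL and anxiety form a secondary objective (Section 2.2) and the subject of two of the five listed hypotheses. One is that anxiety will be lower with HTIMRT, which needs power to show. The other is that QOL will not differ significantly, a result that an imprecise test makes easier to obtain. Sections 14.2 and 14.5 also allow psychosocial results to be reported before the primary endpoint, and this t-test is the only fully specified comparison of mean scores.

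The significance test of baseline scores adds nothing. Under randomization any baseline difference is due to chance, and percent improved is undefined at baseline.

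**Working it through.** **The plan's own figure.** Section 14.2 gives 36 per arm, 52.5% versus 22.5%, one-sided Fisher's exact test at 5%, 80% power. Exact enumeration gives 80.3%, so the figure reproduces. It concerns the primary endpoint; the documents state no power or sample size for QOL.

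**Inputs for the QOL check.**
- n = 36 per arm (72 evaluable, Section 14.2); also 38 per arm (all 76 enrolled).
- One-sided 5% test (Section 14.5).
- Difference of 0.5 SD: illustrative, not in the documents.
- Correlation r between baseline and end-of-RT score: not in the documents; assumed range 0.2 to 0.7.

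**Unadjusted t-test.** The noncentrality is 0.5/√(2/36) = 2.12 on 70 degrees of freedom, with critical value 1.667. Power is 68%. The difference detectable with 80% power is 0.59 SD.

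**ANCOVA.** Residual variance is (1 − r²) times the unadjusted variance. The cost of estimating one slope is a factor of 1 + 1/(2n − 4) = 1 + 1/68 and one degree of freedom. At r = 0.5, for example, the SD is √(0.75 × 1.0147) = 0.872, the noncentrality is 2.12/0.872 = 2.43, and power is 78%.

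| r | Variance removed (r²) | Power at 0.5 SD | Difference detectable at 80% power | Equivalent n per arm, 36/(1 − r²) |
|---|---|---|---|---|
| unadjusted | – | 68% | 0.59 SD | 36 |
| 0.2 | 4% | 69% | 0.58 SD | 37.5 |
| 0.3 | 9% | 71% | 0.57 SD | 40 |
| 0.5 | 25% | 78% | 0.52 SD | 48 |
| 0.7 | 49% | 90% | 0.43 SD | 71 |

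A simulation of 20,000 trials with 36 per arm gave ANCOVA-to-unadjusted variance ratios of 0.76 at r = 0.5 and 0.53 at r = 0.7, so the gain survives estimation of the slope. At r = 0, where baseline is useless, ANCOVA power is 67%, a loss of less than one point.

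**All 76 patients.** With 38 per arm, power is 70% unadjusted and 80% adjusted at r = 0.5.

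**Carry-over of imbalance.** One standard error of the baseline difference is √(2/36) = 0.24 SD. With equal SDs, the expected shift in the raw end-of-RT difference is r times the imbalance: 0.5 × 0.236 = 0.12 SD at r = 0.5 and 0.7 × 0.236 = 0.16 SD at r = 0.7.

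**Change scores as an alternative.** The variance of a change score is 2(1 − r) times that of the raw score: 1.0 at r = 0.5, 1.4 at r = 0.3. A t-test on change therefore gains nothing at r = 0.5 and loses below it.

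**The case against.** The strongest reply is that the correlation is unknown and could be low. The second questionnaire falls in the last week of RT, when acute reactions are present, and some patients start androgen deprivation before baseline and others after it. At r = 0.2 or 0.3 the gain is only one to three points of power. This stands, and it is why a range is shown. It is not a reason to keep the t-test, because ANCOVA costs less than one point even at r = 0.

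A second reply is that mixed models are already planned. They could recover the precision if baseline is a covariate, or a response constrained to be equal across arms. The plan does not say so, and with complete data an unconstrained arm-by-visit model gives essentially the same end-of-RT contrast as the raw t-test.

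A third is that adjustment for the randomization factors is already allowed. That is correct, and the gap is confined to the baseline score.

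Four stronger readings are tempting, and the documents do not support them:
- A reader might infer that the comparison is biased or invalid. Randomization keeps the t-test valid.
- A reader might infer that baseline is ignored altogether. The percent-improved test in the same sentence uses it, where criteria for meaningful change exist.
- A reader might infer that baseline imbalance passes in full into the result. The expected carry-over is r times the imbalance.
- A reader might compute power two-sided, which gives 55% unadjusted and 67% to 83% adjusted at r = 0.5 to 0.7. Section 14.5 makes arm comparisons one-sided.

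Finally, the hypothesis of no significant QOL difference has no stated margin. ANCOVA narrows the interval but does not supply one.

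**Conclusion.** The point holds as a loss of precision on a secondary endpoint. The only comparison of mean scores with a stated test does not use a baseline measurement that is scheduled for all patients, and the plan does not say whether the mixed models use it. Under the plan's one-sided 5% rule, with 36 per arm and a 0.5 SD difference, baseline adjustment raises power from 68% to between 69% (r = 0.2) and 90% (r = 0.7). Both the difference and the correlation are assumptions, and completeness of the baseline forms is scheduled rather than assured. The primary endpoint, its sample size and its conclusion are unaffected. This is a free improvement, not an error that invalidates a result.

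**What to change.** In Section 14.5:
1. Replace the t-test at treatment completion with ANCOVA: end-of-RT score on arm, baseline score and, where strata sizes allow, the randomization factors. Eight strata in about 72 patients may be sparse, so main effects of the three factors are the practical choice.
2. State that the mixed models adjust for baseline score.
3. Keep the percent-improved summary and its Fisher's exact test, for post-baseline visits only.
4. Describe baseline scores by arm without a significance test.

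The cost is a few lines of SAP wording. No new data, visits or patients are needed.
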